12.3 Pregnancies

Pregnancy data will be shown in a data listing. No special analysis will be performed on the pregnancy data. Patients are to be discontinued from the study if they become pregnant.

12.4 Clinical Laboratory Evaluations

Liver function test results (ALTs) will be presented both graphically and in tables.

Descriptive summaries (median, 1st quartile, 3rd quartile, minimum, and maximum) of values at baseline, 2, 4, 6, 8, 10, 12, 16, 20, 24, 28, 36 & 52 weeks will be presented by treatment for the Safety Population.

The number of patients with clinical laboratory values above the normal range pre-procedure versus post-procedure will be tabulated for the Safety Population by treatment group.

Values that are outside the normal range will also be flagged in the data listings, along with the corresponding normal range. Any out-of-range values that are identified by the investigator as being clinically significant will also be shown in a data listing.

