EXCL11.	Patients with known significantly impaired bone marrow function as for example significant anaemia, leukopaenia, neutropaenia or thrombocytopaenia as shown by the following laboratory values at the time of screening: 

• White blood cells < 3000 x 10^6/L;

• Platelets < 125 x 10^9/L;

• Haemoglobin < 9.0 g/dL for males and < 8.5 g/dL for females.

EXCL12.	Patients with a history of latent or active TB prior to screening will not be eligible. For exceptions, refer to inclusion criteria (INCL6 group).

EXCL13.	
Subjects must undergo screening for hepatitis B and C virus (HBV, HBC). At a minimum, this includes testing for Hepatitis B surface antigen (HBsAg), Hepatitis B core antibody (anti-HBc) and Hepatitis C antibody (Anti-HCV Ab),
 

• Subjects who test positive for surface antigen (HBsAg+) are not eligible for this study, regardless of the results of other hepatitis B tests.

• Subjects who test negative for surface antigen (HBsAg-) and test positive for core antibody (anti-HBc+) are eligible for this study provided that the HBV DNA test is done. All subjects who test positive for core antibody (anti-HBc+) must undergo further testing for hepatitis B deoxyribonucleic acid (HBV DNA test).

○ If the HBV DNA test is positive, the subject is not eligible for this study.

○ If the HBV DNA test is negative, the subject is eligible for this study.

• In the event the DNA test cannot be performed, the subject is not eligible for the study.

EXCL14.	Primary or secondary immunodeficiency (history of or currently active) unless related to primary disease under investigation.
EXCL15.	Pregnancy, lactation (nursing) or women of child-bearing potential (WCBP) unwilling to use an effective birth control measure (see appendix 1 ) whilst receiving treatment and after the last dose of protocol treatment as indicated in the relevant SmPC.
EXCL16.	Men whose partners are of child-bearing potential but who are unwilling to use an effective birth control measure whilst receiving treatment and after the last dose of protocol treatment as indicated in the relevant SmPC.

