### 7.10 Withdrawal of trial treatment

Patients showing an unacceptable degree of disease activity (not achieving a PsARC response) beyond week 12 and before the week 24 assessment may be withdrawn from study medication (i.e.: trial intervention) at the discretion of the chief investigator (or medically-qualified delegate) and treated as clinically indicated. At week 24 patients with MDA will continue with their allocated treatment and undergo further assessments as per protocol (see [section 5.1](#)).

Patients **MUST** be withdrawn from the study treatment if any of the following occur:

- Pregnancy
- Grade 4 or 5 systemic toxicity (see [appendix 2](#)) or a serious adverse event (SAE) thought to be related to study treatment and not alleviated by symptomatic treatment after cessation of the IMP for up to 2 weeks.
- Recurrent serious infection requiring parenteral (intravenous or intramuscular) antimicrobial agents or hypotension suggestive of impending sepsis syndrome.
- Confirmed blood dyscrasia or a demyelinating disorder (such as multiple sclerosis or optic neuritis)
- Lack of patient compliance with the trial intervention ([section 7.3](#))
- If missing 2 or more consecutive IMP doses.
- When visit attendance during period 1 of the trial (between week 0 and week 24) is delayed by more than 10 days of the mandated window visit date (see also timeline reference in the summary schedule of study assessments, [section 8.6](#))

REC: 14/EM/0124

- Withdrawal of consent (during either interventional period or observational period, see [section 8.6](#))
- Chief Investigator decision

All patients recruited to this study, irrespective of therapy change (as outlined above) will continue to be followed up for the 52 week study duration with imaging and immunological studies as per protocol, with the exception of those who withdraw consent to continue with study assessments.

As far as possible, all examinations scheduled for the final study day must be performed on all subjects who receive the investigational product but do not complete the study according to protocol.

The investigator must make every effort to contact subjects lost to follow-up. Attempts to contact such subjects must be documented in the subject's records (e.g., times and dates of attempted telephone contact, receipt for sending a registered letter).

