Biochemistry (including CRP) / Haematology, ESR	X	X	X	X	X	X	X	X	X	X	X	X	X	
Immunology tests  : ANA (including dsDNA) anti-CCP and RF	X										X	X	X	
Blood and urine collection for biomarkers (Biological Sub-study)		X			X			X		X	X	X	X	
Urinalysis 	X													
Pregnancy test 	X													
Whole-Body MRI (WB-MRI) 	X							X		X		X 	X 	

Study Period	Period 1: Double-blind randomised									Period 2: Observational*				Withdrawal visit **
	Screen	Baseline	(Safety)	(Safety)	Secondary outcome	(Safety)	(Safety)	Primary outcome	(Safety)	Secondary outcome	End of study visit	Extra Visit		
Study Phase														
Week	-4 to 0	0	4 (±7 days)	8 (±7 days)	12 (±7 days)	16 (±7 days)	20 (±7 days)	24 (±7 days)	28 (±7 days)	36 (±7 days)	52 (±7 days)	Y***	X	
Visit number	1	2	3	4	5	6	7	8	9	10	11	98	99	
Musculoskeletal US scan 	X				X			X		X		X 	X 	
Chest-X-ray  , ECG	X													
Plain X-ray of Hands and Feet 	X													
X-ray of the orbits 	X													
Physician VAS global disease Activity	X	X			X			X		X	X	X	X	
Physician Likaert scale, articular disease Activity	X	X		X	X			X		X	X	X	X	
Patient VAS global disease Activity	X	X			X			X		X	X	X	X	
Patient VAS articular pain	X	X			X			X		X	X	X	X	
Patient Likaert scale, articular disease Activity	X	X		X	X			X		X	X	X	X	
HAQ	X	X			X			X		X	X	X	X	
DLQI	X				X			X		X	X	X	X	
SF-36	X	X			X			X		X	X	X	X	
ASQoL	X				X			X		X	X	X	X	
BASDAI		X			X			X		X	X	X	X	
Administration of SC IMP 		X	X	X	X	X	X	X						

**1.** At screening visit; end of study visit (visit 11, week 52); extra visit (week Y); and withdrawal visit (week X), immunology tests should not be repeated if results available within 20 days prior to study visit.

If subjects do not have a chest x-ray or hands/feet x-ray performed within 3 months of screening, an x-ray should be performed after it is certain the subject meets the inclusion/exclusion criteria (in order to minimize exposure to x-ray radiation).

X-ray of the orbits should be performed only in subjects contraindicated to WB-MRI, who report a personal history suggestive of metallic fragments present in the orbits.

**2, 3.** Urinalysis and Pregnancy test can be repeated in other visits as clinically indicated.

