## **8.9 Safety/Monitoring Visit (week 4, $\pm 7$ days)**

- Confirmation of on-going consent
- Review of previous blood results/reports (from Week 2 – Baseline visit).
- Adverse events evaluation.
- Concomitant medication.
- Duration of articular morning stiffness.
- PsA-related comorbidities.
- Vital signs (blood pressure after a 5-minute rest, pulse rate and body temperature).
- Measurement of body weight.
- Blood tests:
  - Haematology, blood chemistry.
  - CRP and ESR.
- Compliance assessment.
- Dispense study drugs according to treatment arm. MTX (oral or SC) to be increased to 25 mg ([section 7.3](#)).

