	8.6		Added clarification that the assessment of predictors/modifiers of treatment response will be made for response at 24 weeks	27/06/2023
	8.7		Typo in derivation of PASDAS corrected Typo in range of LDI corrected; description of calculation expanded to match development paper MDA criterion corrected to include BSA, to match development paper Joint and enthesal remission criteria corrected to match protocol Definitions of CPDAI 'not involved' category added; typos in criteria for scores of 2 & 3 corrected	20/06/2023 20/06/2023 20/06/2023 20/06/2023 20/06/2023
	9.2		Key exclusion criteria for derivation of per protocol population amended to include receipt of systemic steroids within 4 weeks prior to screening	20/06/2023
	11.3		References to exploratory subset analyses using 76/78 joints for the secondary outcomes MDA and ACR response removed, as the intention is to focus solely on PsARC response. Correction to planned correlation between joint counts and total US GLOESS, which will be assessed using screening values rather than baseline values, as US was performed at screening rather than baseline	27/06/2023
	12.4		Initial inspection of ALT results indicates skewed distributions, therefore the planned summaries have been amended accordingly, and details given as to the time-points at which the values will be summarised. References to changes from baseline have been removed in favour of summaries at each time-point.	
8.0	4.0	3.2.4	Unplanned endpoints i.e. PASDAS status and response variables, published since the inception of the trial, added in a separate section: 
• Very low disease activity (PASDAS<1.9)• PASDAS moderate or good response• PASDAS meaningful change value achieved (improvement >1.29)	09/11/2023 (post-unblinding)
	8.7		Unplanned PASDAS status and response variables, and sensitivity definitions of US remission, defined in the derived variable section	09/11/2023 (post-unblinding)

Protocol version	Updated SAP n ^o	Section changed	Description of and reason for change	Date changed
	11.4		New 'Additional unplanned analysis' section added to give details of analysis methods for unplanned endpoints and unplanned descriptive summaries	09/11/2023 (post-unblinding)

APPROVALS

Approved By:

Role: Chief Investigator

Name: [name]

Date: 17/11/2023

Signature: _____

Role: Sub-Investigator

Name: [name] [name]

Date: 17 – November - 2023

Signature: _____

Role: Trial statistician; SAP author

Name: [name]

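### No planned laboratory table counts low blood counts by arm: the abnormal-value table in SAP 12.4 looks only above the normal range, ALT is the only analyte named, and its pre/post comparison is undefined

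*SAP*

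**What the plan says.** SAP 12.4 plans three kinds of laboratory output.

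- **ALT summaries.** The section opens with "Liver function test results (ALTs) will be presented both graphically and in tables". It then plans medians, quartiles and extremes by visit and treatment. That sentence does not repeat the analyte, but the SAP revision history entry for 12.4 ties it to ALT: "Initial inspection of ALT results indicates skewed distributions, therefore the planned summaries have been amended accordingly".
- **One by-arm table of abnormal results.** The rule is "The number of patients with clinical laboratory values above the normal range pre-procedure versus post-procedure will be tabulated", in the Safety Population and split by arm. No analyte is named, and neither time point is defined.
- **Listings.** Out-of-range values are flagged in either direction, and those the investigator judges clinically significant are listed.

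The other adverse-event tables by arm cover SAEs (SAP 12.2.1) and AEs leading to withdrawal (SAP 12.2.2). SAP 12.2.4 rules out any further AE analysis. Protocol 11.6 plans SAE summaries and no laboratory table.

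On the collection side, the row "Biochemistry (including CRP) / Haematology, ESR" in protocol 8.6 is marked at every visit. Protocol 6.3.1 (INCL6.7) sets lower limits at entry for haemoglobin, white cells, neutrophils and platelets. Protocol 6.3.3 excludes "Patients with known significantly impaired bone marrow function as for example significant anaemia, leukopaenia, neutropaenia or thrombocytopaenia". Protocol 7.10 lists "Confirmed blood dyscrasia or a demyelinating disorder" among the events that require withdrawal from study treatment.

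**The concern.** Anaemia, leukopenia, neutropenia and thrombocytopenia all lie below the normal range. The planned comparative table looks only above it, and the section names only a liver enzyme. The trial compares golimumab plus methotrexate with methotrexate plus placebo, so whether low counts are more frequent on the combination is a natural safety question, and the data to describe it are collected in both arms. Under the plan as written, a reader who wanted that comparison would have to count patients by hand from the listings.

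The phrase comparing values before and after a procedure adds a second problem. There is no procedure: injections are given every four weeks over a 24-week blinded period, followed by observation to week 52. The SAP does not say whether the later value is the last, any or the worst one, so two programmers could produce different tables from the same data, even for ALT.

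**Working it through.** No power or effect-size arithmetic applies. The check is to trace where a low blood count could appear in each planned output.

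**Step 1: the abnormal-value table under each reading (SAP 12.4).**

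| Reading of the table | Is a low haematology value counted? | Why |
|---|---|---|
| All analytes | No | Only values above normal are counted |
| ALT only | No | Haematology is not in the table |

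The conclusion is the same on both readings, although the defect differs: wrong direction on the first, missing analytes on the second.

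**Step 2: the by-visit summaries (SAP 12.4).** With the revision history, these are ALT summaries. Even if they were read to cover every analyte, they would give the lowest value in each arm at each visit, not the number of patients below normal.

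**Step 3: the adverse-event tables.** Protocol 9.1 allows an abnormal laboratory finding to be an AE, so this route is open in part.

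| Low count is recorded as | By-arm count? | Source |
|---|---|---|
| SAE | Yes | SAP 12.2.1 |
| AE leading to withdrawal | Yes | SAP 12.2.2 |
| Any other AE | No | SAP 12.2.4 |
| Laboratory value only | No; listings only | SAP 12.4 |

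**Step 4: what is left.** The gap is the last two rows: low counts that are neither serious nor a cause of withdrawal. It applies to four values: haemoglobin, white cells, neutrophils and platelets.

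**Step 5: time points (minor).** The ALT summary lists baseline and weeks 2, 4, 6, 8, 10, 12, 16, 20, 24, 28, 36 and 52, which is 13. From baseline on, the protocol 8.6 schedule has timed visits at weeks 0, 4, 8, 12, 16, 20, 24, 28, 36 and 52, which is 10. The difference, 13 − 10 = 3, is weeks 2, 6 and 10. Protocol 8.9 nevertheless asks for a "Review of previous blood results/reports (from Week 2 – Baseline visit", and protocol 5.1 provides for blood monitoring under local guidelines. Those tests may therefore exist outside the 8.6 grid. The sections need to agree on this, but it does not show that data are missing.

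**The case against.** Several objections deserve weight.

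- **The by-arm report is not blind to low counts.** A reader might infer that it would show none whatever the data. The documents do not support that: a low count that is an SAE, or that is recorded as an AE leading to withdrawal, is tabulated by arm. Confirmed blood dyscrasia, as a mandatory reason to stop, should reach the second of these tables if recorded in that way. This stands and limits the point.
- **Looking above normal may be correct.** If the sentence was meant for ALT, the direction is right. A reader might expect the table to print false zeros for low counts in both arms. On the ALT reading there would be no haematology rows at all, so no zeros. This stands, but it leaves haematology without a by-arm summary.
- **The protocol does not name every low count as an on-treatment risk.** The limits in 6.3.1 and 6.3.3 are entry criteria with their own cut-offs, the stopping term is confirmed blood dyscrasia, and 7.7 only refers to the SmPC. This stands. Those sections show that low counts matter to the protocol's safety thinking, not that any value below normal is a stopping event.
- **The SAP does not say that a single later value is used.** True. The fault is that the comparison is undefined, not that on-treatment values are known to be ignored.
- **Laboratory values are not among the listed safety variables** in protocol 4.3 or SAP 3.3.3. This is fair, but SAP 12.4 does plan a by-arm laboratory table, and what that table covers should be stated.

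**Conclusion.** The point holds in limited form. No planned laboratory table counts low haemoglobin, white cells, neutrophils or platelets by arm, and a low count that is neither an SAE nor an AE leading to withdrawal has no by-arm count in any planned output. The pre/post comparison is undefined for every analyte, ALT included.

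This rests on the text of SAP 12.1 to 12.4 and protocol 11.6 and does not depend on which reading of the abnormal-value table is right. How many patients fall into the gap cannot be known from the documents, so no effect in patient numbers is claimed. The change is worth making because a comparative safety report would otherwise be incomplete on values the trial measures at every visit. The primary and secondary efficacy results are unaffected.

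**What to change.** Replace the abnormal-value sentence in SAP 12.4 with a specification along these lines:

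- Analytes: at least haemoglobin, white cells, neutrophils, platelets and ALT.
- Population and layout: Safety Population, by treatment group, one block per analyte.
- Count: patients below and, separately, above the normal range at baseline against the worst post-baseline value, taking the lowest value for the low side and the highest for the high side.
- Periods: up to and including the week 24 visit, and after week 24, so that no value is counted in both.
- Denominator: patients with a baseline value and at least one value in the period.

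Separately, as a minor item, reconcile weeks 2, 6 and 10 between SAP 12.4 and protocol 5.1, 8.6 and 8.9.

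No new visits, samples or tests are needed. The cost is a few extra descriptive rows. SAP version 4.0 post-dates unblinding, so a table added now should be labelled as such, in the same way as the unplanned descriptive summaries in SAP 11.4.

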INCL6.4.	Have confirmed either: 

▪ Within 6 weeks prior to the administration of study agent, a negative QuantiFERON-TB Gold test result;

or

▪ Within 12 weeks from a newly identified positive QuantiFERON-TB Gold test result (in which active TB has been ruled out) and for which appropriate treatment for latent TB has been initiated either prior to, or simultaneously with, the first administration of study agent.

INCL6.5.	In the event of 2 indeterminate QuantiFERON-TB Gold in-tube tests results, the subjects will be treated as if having latent TB prior or simultaneously with the first administration of study agent.
INCL6.6.	Have a chest radiograph (posterior-anterior view), read by a qualified radiologist, whose diagnostic assessment is consistent with no evidence of current active TB or old inactive TB, and taken within 12 months of the study.
INCL6.7.	Have a screening laboratory test result as follows: 

INCL6.7.1. - Hb<math>\geq</math>8.5 g/dL or <math>\geq</math>5.3 mmol/L

INCL6.7.2. - White blood cell (WBC) count <math>\geq</math>3.5<math>\times</math>10<math>^3</math> cells/uL

INCL6.7.3. - Neutrophils <math>\geq</math>1.5 <math>\times</math>10<math>^3</math> cells/uL

INCL6.7.4. - Platelets <math>\geq</math>100<math>\times</math>10<math>^3</math> cells/uL

INCL6.7.5. - Serum alanine aminotransferase (ALT) and aspartate aminotransferase (AST) levels not exceeding 1.5 times the upper limit of normal (ULN) for the central laboratory conducting the test.

INCL6.7.6. - Serum creatinine not exceeding 1.5 mg/dL

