### 6.3.3. Exclusions for general safety

EXCL3.	Patients with significant concurrent medical diseases including uncompensated congestive heart failure, myocardial infarction within 52 weeks from screening, unstable angina pectoris, uncontrolled hypertension (BP>160/95), severe pulmonary disease, or history of human immunodeficiency virus (HIV) infection, immunodeficiency syndromes, central nervous system (CNS) demyelinating events suggestive of multiple sclerosis, renal or gastrointestinal conditions, which in the opinion of the investigator places the patient at an unacceptable risk for participation in the study or would make implementation of the protocol difficult.
EXCL4.	Patients with cancer or a history of cancer (other than resected cutaneous basal cell carcinoma, and in situ cervical cancer) within 5 years of screening.
EXCL5.	Patients with current crystal or infective arthritis.
EXCL6.	Patients with chronic infection of the upper respiratory tract (e.g. Sinusitis), chest (e.g. Bronchiectatic lung disease), urinary tract or skin (e.g. Paronychia, chronic ulcers, open wounds) within 4 weeks of screening.
EXCL7.	Patients who have a chest radiograph within 3 months prior to the first administration of study agent that shows an abnormality suggestive of a malignancy or current active infection, including (but not limited to) TB, histoplasmosis or coccidioidomycosis.
EXCL8.	Patients with any ongoing or active infection or any major episode of infection requiring hospitalization or treatment with IV antibiotics within the preceding 30 days of screening and/or orally administered antibiotics in the preceding 15 days of screening.
EXCL9.	Patients with abnormal liver function including known liver cirrhosis, fibrosis, or known alcoholic steatohepatitis (NASH) at the time of screening or abnormal blood tests as shown by: 

• Aminotransferase (AST) / alanine aminotransferase (ALT) > 3x ULN, OR

• Bilirubin >51umol/L.

EXCL10.	Patients with known severe hypoproteinaemia at the time of screening, e.g.: in nephrotic syndrome; OR impaired renal function, as shown by: Serum Creatinine > 133 $\mu$ mol/L.

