## 9.6 Recording and reporting of AEs

### 9.6.1 Recording and reporting of all AEs

Determination of AEs should be based on the signs or symptoms detected during the physical examination and on clinical evaluation of the subject, and should be assessed and recorded at every visit. Signs and symptoms must be recorded using standard medical terminology.

AEs and SAEs will be collected from first dose of protocol treatment until week 52 (visit 11). The Investigator must instruct the subject to report AEs and SAEs during this time period.

**All adverse events must be evaluated by a medically qualified and authorised member of the study research team, and graded (in terms of severity) in accordance with the Common Terminology Criteria for Adverse Events (CTCAE) (see [appendix 2](#)).**

During the time period specified above, the Investigator will:

- Record all AEs and SAEs on source documents.
- Record all AEs and SAEs in the eCRF for subjects who are not screen failures.
- Report all SAEs on a 'Serious Adverse Event/Expedited Report from a Clinical Trial'. Instructions on where to send this form will be provided by the Sponsor.

The Investigator must follow up on all AEs and SAEs until the events have subsided, returned to baseline, or, in case of permanent impairment, until the condition has stabilized whilst the subject remains under follow up as per study protocol. All adverse events that are still ongoing when the patient finishes study follow-up will be coded as 'ongoing' in the eCRF, after which time appropriate follow up will be organized as per standard clinical care.

The Sponsor will maintain detailed records of all AEs and SAEs reported by an Investigator in accordance with good clinical practice and applicable local regulations.

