8.2 Methods for Withdrawals, Missing Data, and Outliers

For missing values at baseline, screening values (if available) will be carried forward.

Visits which fall outside ± 14 days of the scheduled date will be considered missing for analysis.

For patients who withdraw early, in the primary analysis data from the withdrawal visit will be imputed for subsequent visits for continuous outcomes, and non-response will be imputed for binary outcomes.

Multiple imputation by chained equations will be used to address the remainder of the missing data for primary and secondary outcomes. The number of imputed datasets will be determined by the Monte Carlo (MC) error rate of the resulting combined estimates. A minimum of 20 datasets will be imputed; if the MC errors calculated for the coefficient and standard error for the treatment group term are more than 10% of the estimated standard error the number of imputations will be increased in increments of 5 until the MC error is <10% of the standard error. Continuous interval, count or ordinal outcomes will be imputed using predictive mean matching to 10 nearest neighbours; categorical outcomes will be imputed using binary, ordinal or multinomial logistic regression as appropriate to the data type. Composite measures, including the primary outcome, and the achievement of thresholds of response (e.g. PsARC) will be computed passively following imputation of the underlying score or components, provided sample size is sufficient for the imputation models to converge. If the number of parameters to be estimated exceeds the number of patients, these variables will be directly imputed.

All imputation models will include:

Age at baseline, sex, oligo/polyarticular disease, treatment arm, symptom duration at baseline, baseline values of the variables being imputed (values of components for response variables), other auxiliary variables found to be associated with the outcome to be imputed and/or with the likelihood that it is missing. Only values from the main primary and secondary endpoints (12, 24, 36, 52 weeks) will be included in imputation models. If imputation models continue to fail, mixed modelling will be explored as an alternative – see section 11.2 for details.

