12.2.4 Other AE Assessments

No additional Adverse Event analysis is planned.

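### SAP 12.4 counts patients with values above normal before and after an undefined procedure, and no planned output counts by arm how many patients had a marked ALT rise

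*SAP*

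**What the plan says.** SAP 12.4 plans these outputs for ALT:

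- Graphs, with content not specified.
- By-visit tables by treatment in the Safety Population: "Descriptive summaries (median, 1st quartile, 3rd quartile, minimum, and maximum) of values at baseline, 2, 4, 6, 8, 10, 12, 16, 20", continuing to weeks 24, 28, 36 and 52. That is 13 time points, 12 of them after baseline.
- One count by treatment group: "The number of patients with clinical laboratory values above the normal range pre-procedure versus post-procedure will be tabulated".
- Listings in which out-of-range values are flagged with the normal range. In addition: "Any out-of-range values that are identified by the investigator as being clinically significant will also be shown in a data listing".

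For adverse events, SAP 12.2.1 and 12.2.2 tabulate serious events and events leading to withdrawal by arm, System Organ Class and Preferred Term. SAP 12.2.3 lists deaths. SAP 12.2.4 then closes the section: "No additional Adverse Event analysis is planned". Protocol 9.6.1 requires every adverse event to be "graded (in terms of severity) in accordance with the Common Terminology Criteria for Adverse Events (CTCAE"), but neither document plans a by-arm table of those grades. Protocol 11.6 covers serious events only.

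The protocol uses ULN multiples for ALT at entry only. INCL6.7.5 requires ALT and AST "not exceeding 1.5 times the upper limit of normal (ULN"), while EXCL9 excludes values above 3 x ULN.

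**The concern.** ALT is the only laboratory measure that SAP 12.4 names, and methotrexate is given in both arms. The natural safety question is how many patients in each arm had a marked rise at any time on study. No planned table answers it.

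The one patient-level count has two faults. First, before and after a procedure has no meaning in a drug trial with repeated visits, and the SAP does not say whether the later value is any value, the last or the worst. Second, it has one cut, at the edge of the normal range. A value just above ULN and a value several times ULN fall in the same cell. Because INCL6.7.5 admits patients up to 1.5 x ULN, some may already be in that cell before treatment.

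Biochemistry is also taken at the withdrawal visit (X) and the flare visit (Y) under Protocol 8.6, 8.15 and 8.16. Neither is among the weeks listed in SAP 12.4, and the SAP does not say that their values will be assigned to one.

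At stake is whether a reader of the trial report can compare the arms on non-serious ALT rises that did not end treatment.

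**Working it through.** **Arm size.** SAP 6 gives 84 patients, 42 per group. Check: n per arm = 2 x (1.960 + 0.842)^2 x 1.57^2 / 1^2 = 38.7, so 39 per arm and 78 in total. 78 / 0.95 = 82.1, so 83, made even at 84. The plan's figure reproduces. It matters here only as the arm size.

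**What each by-arm output can show.**

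- Quartiles: the middle of the distribution at a visit.
- Minimum and maximum: one patient each per visit.
- Count above normal: patients above 1 x ULN, with no severity.
- Serious events and events leading to withdrawal: patients by event term, only for events of that kind.
- Listings: every flagged value, but no totals by arm.

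Neither document has a count by ULN multiple, a worst value per patient or a severity shift table.

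**Quartiles.** With 42 values, 0.75 x 42 = 31.5, so the upper quartile is the 32nd ordered value. The 42 - 32 = 10 values above it can take any size without moving the quartiles or the median. An interpolating definition of the quartile also gives 10. Only the maximum responds.

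**Count above normal.** Assume that ULN is the 97.5th percentile, that treatment has no effect, and that the later value means any of the 12 post-baseline results. The chance of at least one result above ULN is 2.5% if the 12 are fully correlated and 1 - 0.975^12 = 26.2% if they are independent. In 42 patients that is 42 x 0.025 = 1 to 42 x 0.262 = 11 patients counted with no drug effect. As an invented example, 12/42 in each arm gives identical rows even if 5 of the 12 in one arm and none in the other exceed 3 x ULN.

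**Illustration including the maximum.** All inputs are assumed: ULN 40 U/L, median ALT 22 to 28 U/L, log-scale SD 0.35 to 0.45, within-patient correlation 0.5 to 0.7, 12 post-baseline tests, and a six-fold rise at one random visit in 2% of one arm and 12% of the other. The two rates and the six-fold size are single chosen values, and they drive the contrast.

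- The visit median differs between arms by about 0.1 to 0.2 U/L, and the 75th percentile by at most about 0.5 U/L.
- Any value above ULN: 20 to 68% in the low-rate arm, 28 to 71% in the high-rate arm.
- Peak above 3 x ULN: 1 to 2% against 7 to 10%, or under 1 against about 3 to 4 patients per 42.
- Visits at which the arm maximum exceeds 3 x ULN: on average 0.5 to 0.9 against 2.7 to 3.6. The high-rate arm has more such visits in close to nine of ten simulated trials.

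The quartiles and the above-normal count therefore separate the arms poorly. The maxima usually do separate them, without saying how many patients are involved.

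**Precision of a patient count.** Exact 95% intervals at 42 per arm: for 0/42 the upper limit is 1 - 0.025^(1/42) = 8.4%; 1/42 is 2.4% (0.1 to 12.6%); 3/42 is 7.1% (1.5 to 19.5%); 5/42 is 11.9% (4.0 to 25.6%).

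**The case against.** The strongest reply is that SAP 12.4 already reports the tail. The maximum is given by arm at 13 time points, graphs are planned, and every out-of-range value is listed with its normal range. Quartiles are a reasonable description of a skewed variable. Serious liver events and those leading to withdrawal are compared by arm. In a trial of 84 patients this is a choice of presentation. Most of that stands, and it limits the point to the missing patient count and the undefined contrast.

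Three stronger readings are tempting, and the documents do not support them.

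- *That the planned output cannot show liver harm.* The by-visit maxima can, and in the illustration above they usually do.
- *That the SAP drops a liver-injury scale set by the protocol.* The 1.5 x and 3 x ULN figures are entry limits. Severity on study is graded by CTCAE. The entry limits show only that ULN multiples are already used in this trial.
- *That ALT results are lost after week 24 through the analysis window.* SAP 8.2 says: "Visits which fall outside ± 14 days of the scheduled date will be considered missing for analysis". That section deals with withdrawals, imputation and outliers, so carrying the rule over to safety tables is an inference. After week 24, scheduled biochemistry falls at weeks 28, 36 and 52, all of which are listed, and Protocol 8.6 collects no trial data at week 44. Only an unscheduled visit X or Y could fall between the listed weeks.

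Visits X and Y are missing from the by-visit table only. The above-normal count and the listings carry no visit restriction.

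**Conclusion.** The point holds in a limited form, and its severity is minor. The before-and-after-procedure count is undefined in this trial and does not separate slight from large rises. No planned output counts by arm the patients with a marked ALT rise. Non-serious rises that do not lead to withdrawal can be read from listings but are not comparable between arms by severity, and results from visits X and Y have no row in the by-visit table.

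This rests on reading SAP 12.1 to 12.4 and Protocol 9.6, 9.9 and 11.6, and on taking the above-normal count to apply to ALT, as its place in SAP 12.4 implies. The simulated figures show the mechanism under assumed inputs and do not predict this trial's data. The primary analysis and its conclusion are unaffected.

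**What to change.** In SAP 12.4, replace the before-and-after-procedure count with a descriptive by-arm shift table: baseline ALT category against each patient's worst post-baseline ALT category, in multiples of ULN.

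- The trial team fixes the bands as display categories only, with at least one band above 3 x ULN. They carry no rule for treatment or monitoring.
- Take the worst value over all recorded post-baseline ALT results, including visits X and Y.
- Keep the by-visit summaries as supportive and the listings as they are.
- SAP version 4.0 already contains changes made after unblinding, so label this table as added after unblinding, in line with SAP 2 on unplanned analyses.

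Separately, the differing ALT entry limits in INCL6.7.5 (1.5 x ULN) and EXCL9 (3 x ULN) should be reconciled. This review takes no position on which is right.

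The cost is a change of SAP wording and one table from ALT values and normal ranges already needed for the planned listings, with no new samples. The drawback is one more descriptive table with wide intervals at about 42 per arm. It should carry no test and should not be read as evidence of no difference.
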